3.2. Secondary Endpoints

3.2.1. Secondary Endpoint: Maternal Participants

- RSV A- and RSV B-neutralizing antibody titers measured before vaccination, at 2 weeks and 1 month after vaccination, and at delivery.

3.2.2. Secondary Endpoint: Infant Participants

- RSV A- and RSV B-neutralizing antibody titers measured at birth and at 1 month, 2 months, 4 months, and 6 months of age depending on the assigned blood sampling schedule.

CCI

CCI

3.4. Baseline Variables

3.4.1. Baseline Variables: Maternal Participants

Day 1 is defined as the day of vaccination and the start of the reporting period for local reactions and systemic events in the electronic diary (e-diary) for maternal participants.

Laboratory data will be collected for maternal participants only. Data are collected during the screening visit, Visit 0 (-14 to -2 days prior to vaccination), and will be considered baseline data.

Day 1 is considered the baseline visit for the following assessments: immunogenicity, obstetric examination, and vital signs.

3.4.2. Baseline Variables: Infant Participants

Day 1 is defined as the day of birth (Visit 1) for the infant participants.

Day 1 is considered the baseline visit for the following assessments: immunogenicity (cord blood sample collected at birth), physical examination, and vital signs.

3.5. Safety Endpoints

3.5.1. Adverse Events

AEs will be captured and reported in accordance with Pfizer reporting standards.

For maternal participants the time period for actively eliciting and collecting AEs and SAEs (“active collection period”) begins from the time the maternal participant provides informed consent, which is obtained before participation in the study (ie, before undergoing any study-related procedure and/or receiving investigational product), through and including a minimum of 1 month (30 days) after the last administration of the investigational product. In this study, the investigator and site staff will ensure the active elicitation and collection of AEs and SAEs through 1 month after vaccination. From 1 month after vaccination until the maternal participant completes the study, MAEs and SAEs will be collected.

For infant participants, the time period for actively eliciting and collecting AEs and SAEs (“active collection period”) begins at birth and continues through and including a minimum

of 28 days after birth. From Visit 2 until the last study visit, only AEs of special interest, MAEs, and SAEs, including hospitalizations, will be reported.

For maternal participants who are screen failures, the active collection period ends when screen failure status is determined. If the participant withdraws from the study and also withdraws consent for the collection of future information, the active collection period ends when consent is withdrawn.

During the active collection period, both nonserious AEs and SAEs are recorded on the case report form (CRF) and will be categorized according to the current version (at the time of reporting) of the Medical Dictionary for Regulatory Activities (MedDRA).

An immediate AE is defined as any AE that occurred within the first 30 minutes after administration of the investigational product for maternal participants.

An MAE is defined as a nonserious AE that results in an evaluation at a medical facility. From Visit 2 (for infant participants) or from 1 month after vaccination (for maternal participants) until the participant completes the study, MAEs and SAEs will be collected.

AEs of special interest for infant participants are major congenital anomalies and developmental delays and are collected from birth through the end of the study (12-month-of-age visit).

CCI

In addition, AEs occurring up to 48 hours after blood draws or collection of nasal swabs that are related to study procedures must be reported in the CRF.

A 3-tier approach will be used to summarize AEs. Under this approach, AEs are classified into 1 of 3 tiers. Different analyses will be performed for different tiers (see [Section 6.6.1](#)).

Tier 1 events: These are prespecified events of clinical importance and are maintained in a list in the product's Safety Review Plan.

Tier 2 events: These are events that are not Tier 1 but are "common." A MedDRA preferred term (PT) is defined as a Tier 2 event if there are 4 or more participants in any vaccine group reporting the event within 30 days.

Tier 3 events: These are events that are neither Tier 1 nor Tier 2 events.

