- If ≥ 2 RSV-vaccinated maternal participants experience premature labor or premature rupture of membranes within 14 days after vaccination.
- If ≥ 4 RSV-vaccinated maternal participants report the same or similar severe (Grade 3) AE within 7 days after vaccination, assessed as possibly related by the investigator, or for which there is no alternative, plausible, attributable cause.

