9.4.2. Safety Analyses

Endpoint	Statistical Analysis Methods
Primary	
 • The point estimate and exact 2-sided 95% CI will be calculated using the Clopper-Pearson method for the percentage of participants reporting each event for each vaccine group. • A 3-tier approach will be used to summarize AEs. For both Tier 1 and Tier 2 events, the 95% CIs for the difference in percentage of participants reporting the events between the RSV vaccine group and the placebo group will be calculated using the test statistic proposed by Miettinen and Nurminen; in addition, for Tier 1 events, the asymptotic p-values will also be presented for the difference in percentage of participants reporting the events, based on the same test statistic and under the assumption that the test statistic is asymptotically normally distributed. There is no preidentified Tier 1 event for this study. A Medical Dictionary for Regulatory Activities (MedDRA) preferred term is defined as a Tier 2 event if there are 4 or more participants in at least 1 vaccine group reporting the event. 
The safety analyses are based on the safety population. Participants will be summarized by the vaccine group corresponding to the vaccine they (for maternal participants) or their mothers (for infant participants) actually received. Missing e-diary data will not be imputed; missing AE dates and missing AE intensity will be addressed using the Pfizer safety rules.

Secondary	
 • Not applicable (N/A)
CCI	

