6.1.1.3. AEs Within 1 Month After Vaccination

- Analysis set: Safety ([Section 4](#)).
- Analysis methodology: Descriptive summary statistics for Tier 3 events; difference and 95% CI between the vaccine group and the placebo group for Tier 2 events.
- Intercurrent events and missing data: For participants who discontinue, all collected data will be included; missing AE dates will be imputed as described in Pfizer's Vaccine Statistics Rulebook.
- For each group, number of participants with AEs within 1 month (30 days) (n), %, and 95% CI will be presented for any AE, each system organ class (SOC), and each PT within each SOC, by vaccine group. For AEs classified as Tier 2 events, difference in proportions and associated 2-sided 95% CI between the vaccine group and the placebo group will be presented.

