6.1.1.4. Obstetric Complications, MAEs, and SAEs Throughout the Study

- Analysis set: Safety ([Section 4](#)).
- Analysis methodology: Descriptive summary statistics.
- Intercurrent events and missing data: For participants who discontinue, all collected data will be included; missing AE dates will be imputed as described in Pfizer's Vaccine Statistics Rulebook.
- For each group, number of participants with obstetric complications, MAEs, and SAEs throughout the study (n), %, and 95% CI will be presented for any event, each SOC, and each PT within each SOC, by vaccine group.

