6.1.2.2. AEs Within 1 Month of Age

- Analysis set: Safety (Section 4).
- Analysis methodology: Descriptive summary statistics for Tier 3 events; difference and 95% CI between the vaccine group and the placebo group for Tier 2 events.
- Intercurrent events and missing data: For participants who discontinue, all collected data will be included; missing AE dates will be imputed as described in Pfizer's Vaccine Statistics Rulebook.
- For each group, number of participants with AEs **CCI** within 1 month (30 days) (n), %, and 95% CI will be presented for any AE, each SOC, and each PT within each SOC, by vaccine group. For AEs classified as Tier 2 events, difference in proportions and associated 2-sided 95% CI between the vaccine group and the placebo group will be presented.

6.1.2.3. AEs of Special Interest (Major Congenital Anomalies, Developmental Delays), MAEs, and SAEs Through 12 Months of Age

- Analysis set: Safety (Section 4).
- Analysis methodology: Descriptive summary statistics.
- Intercurrent events and missing data: For participants who discontinue, all collected data will be included; missing AE dates will be imputed as described in Pfizer's Vaccine Statistics Rulebook.
- For each group, number of participants with AEs of special interest, MAEs, and SAEs through 12 months of age (n), %, and 95% CI will be presented for any event, each SOC, and each PT within each SOC, by vaccine group. For AEs of special interest, difference in proportions and associated 2-sided 95% CI between the vaccine group and the placebo group will be presented.

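### The one-month AE analyses specify a placebo contrast only for single preferred terms with 4 or more participants in an arm; any AE, SOC rows and groups of related terms get none

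*SAP*

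**What the plan says.** The gate is set at the level of one coded term in one arm. SAP 3.5.1: "A MedDRA preferred term (PT) is defined as a Tier 2 event if there are 4 or more participants in any vaccine group", counted within 30 days. Protocol 9.4.2 uses the same count: a term is Tier 2 "if there are 4 or more participants in at least 1 vaccine group reporting the event". The other route to a contrast, Tier 1, is empty: "There is no preidentified Tier 1 event for this study".

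For mothers, SAP 6.1.1.3 says that n, % and 95% CI "will be presented for any AE, each system organ class (SOC), and each PT within each SOC, by vaccine group". The contrast is then reserved: "For AEs classified as Tier 2 events, difference in proportions and associated 2-sided 95% CI between the vaccine group and the placebo group". For infants, SAP 6.1.2.2 is parallel: "Descriptive summary statistics for Tier 3 events; difference and 95% CI between the vaccine group and the placebo group for Tier 2 events".

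SAP 6.1.1.4 treats the remaining maternal events the same way, without a difference: "number of participants with obstetric complications, MAEs, and SAEs throughout the study (n), %, and 95% CI will be presented for any event".

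Two infant endpoints are handled differently. Birth outcomes (SAP 6.1.2.1) and AEs of special interest (SAP 6.1.2.3) get a difference and 95% CI with no count threshold. SAP 5.2.1 also allows CIs for differences at the analyst's discretion, without saying for which rows.

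**The concern.** Safety is the primary objective, and the percentage of participants with AEs is a primary estimand for mothers and infants (SAP 2.1.4). Yet a single term with four reports gets a placebo contrast while the headline any-AE row does not. This is the first study of the vaccine in pregnant women, and SAP 2 says its data will decide whether development proceeds and with which dose and formulation.

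The unit of counting matters most for conditions that are coded under several terms. The protocol itself counts two such events together in its stopping rules (8.2.5), where two or more RSV-vaccinated "maternal participants experience premature labor or premature rupture of membranes within 14 days after vaccination" meet a rule. The tier rule looks at each coded term alone. Each term may stay at 3 or fewer, fall to Tier 3 and get no contrast, although the condition as a whole exceeds placebo.

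**Working it through.** **Inputs.** The gate is 4 or more participants with one term in any arm (SAP 3.5.1, Protocol 9.4.2). There are five arms with equal allocation and up to 650 women, so 650/5 = 130 per arm; the note to Protocol Table 6 uses 100 per arm for the northern hemisphere. The CI method for a difference is Chan-Zhang in SAP 5.2.1 and Miettinen-Nurminen in Protocol 9.4.2, so both are shown where available. The documents give no event rates or coding patterns; those below are assumptions.

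**The plan's own figure.** It gives none for the gate. The nearest is Protocol Table 6, which reproduces: 1 − (1 − 0.01)^100 = 0.634, against 0.63 printed.

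**1. The cut-off suits one isolated term.** At 130 per arm, the Chan-Zhang lower limit is about −0.6 points for 3 v 0 and +0.1 points for 4 v 0. So 4 is about where a single term begins to exclude zero.

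**2. The most that can pass under the gate.** If each affected participant has one term and there are k terms, no term reaches 4 only if the arm has at most 3k affected participants. At 3k + 1, some term must reach 4.

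| Terms | Arm v placebo | Difference (points) | 95% CI |
|---|---|---|---|
| 2 | 6/100 v 0/100 | 6.0 | 2.2 to 12.5 (M-N) |
| 3 | 9/100 v 0/100 | 9.0 | 4.8 to 16.3 (M-N) |
| 4 | 12/100 v 0/100 | 12.0 | 7.0 to 19.8 (M-N) |
| 3 | 9/130 v 0/130 | 6.9 | 3.7 to 12.7 (M-N); about 3.2 to 12.6 (Chan-Zhang) |

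All exclude zero, and in none is a difference specified.

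**3. Any AE and SOC rows.** No count ever triggers a difference here. Two illustrations at 100 per arm (Miettinen-Nurminen): any AE at 40 v 20 gives 20.0 points (7.4 to 32.2); an SOC at 18 v 6, with every term at 3 or fewer, gives 12.0 points (3.2 to 21.5).

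**4. How often no term qualifies.** Assume a condition at 5% in an affected arm and 1% on placebo, 130 per arm, split evenly over k terms. For one arm, the chance that no term reaches 4 is the multinomial probability summed over all counts c1,…,ck ≤ 3, with probability p/k per term. At p = 5% this is 0.345, 0.563 and 0.711 for k = 2, 3, 4. At p = 1% it is 0.991, 0.997 and 0.999.

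- One formulation affected, that arm and placebo: 0.345 × 0.991 = 0.34; 0.563 × 0.997 = 0.56; 0.711 × 0.999 = 0.71. Adding the other three arms at 1% changes little (k = 2: 0.342 × 0.991³ = 0.333).
- All four affected: 0.345⁴ × 0.991 = 0.014; 0.563⁴ × 0.997 = 0.10; 0.711⁴ × 0.999 = 0.26.

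**5. What is lost.** In simulation with one affected arm and three terms, the grouped difference excludes zero in 47% of trials, against 31% for any displayed term. In 16% of all trials the group excludes zero and nothing is contrasted. With two terms, as in the stopping-rule pair, that figure is about 7%, and under 0.5% if all four arms are affected.

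**The case against.** The strongest reply is that little is hidden. Any AE, every SOC and every term are tabulated by arm with Clopper-Pearson CIs; 9/130 (3.2% to 12.7%) beside 0/130 (0% to 2.8%) is plain to see wherever such a row exists. The any-AE estimand is defined as a percentage in each vaccine group, so per-arm figures do deliver it, and the study has no hypothesis or decision rule. Obstetric complications are already defined by the sponsor's clinician before unblinding (Protocol 9.4.2.1). The stopping-rule pair is also monitored as a group: once unblinded sponsor personnel confirm that two RSV-vaccinated women had either event within 14 days, randomization and vaccination pause, the internal committee reviews the data and the external committee is informed. All of this stands.

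It does not remove the gap. Two separate intervals do not estimate a difference, and the SAP accepts this by adding differences for Tier 2 terms. A pausing rule is not an analysis of the final data. A set of related terms that is neither an SOC nor the obstetric list has no row at all.

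A reader might infer that an excess of any size can go without a contrast. For a split condition the documents do not support that: the ceiling is 3 participants per term per arm. A reader might also take 56% as the general failure rate. It assumes three terms and one affected formulation out of four; with all four affected it is 10%. Nor can complete absence be asserted: SAP 5.2.1 leaves discretion, and SAP 6.6.1, to which 3.5.1 refers for the tier analyses, is partly blacked out.

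**Conclusion.** The point holds for the visible text, as a low-cost improvement to the primary safety comparison rather than an error that invalidates it. No vaccine-minus-placebo difference is specified for any AE, SOC rows, grouped terms or maternal obstetric complications, MAEs and SAEs. For a condition split over k terms, up to 3k participants in an arm against 0 can go without a contrast.

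The practical size depends on how widely the effect is shared. It is material if one formulation is affected and the coding is spread over three or four terms. It is small if all four are affected and there are two terms. The one-formulation case deserves weight because the study is meant to inform the choice of dose and formulation. The probabilities rest on assumed rates of 5% v 1%, an even split, one term per participant and equal arms of 130. No error rate or sample size changes, because all analyses are descriptive.

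**What to change.** 1. SAP 6.1.1.3 and 6.1.2.2: add the vaccine-minus-placebo difference and 95% CI to the any-AE row and to each SOC row.
2. SAP 6.1.1.4: add the same to the any-event row for the obstetric complications that the study clinician already defines before unblinding.
3. SAP 3.5.1: add a short list of grouped terms, fixed while blinded, and present the difference for each group. The pair of preterm-labor and membrane-rupture events that Protocol 8.2.5 counts together is an obvious entry.
4. Label all of these descriptive and unadjusted, in line with SAP 6.6.1, which makes no multiplicity adjustment.

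The cost is SAP wording, extra columns in existing tables and one blinded list. Data collection and conduct are unchanged. The downside is more unadjusted intervals to read, some of which will exclude zero by chance.

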3.5.2. Reactogenicity Data

Reactogenicity data are prompted AEs collected using an e-diary, during Days 1 through 7, starting on the day of vaccination (Day 1). The reactogenicity data will include local reactions (redness, swelling, and pain at the injection site) and systemic events (fever, fatigue, headache, vomiting, nausea, diarrhea, muscle pain, and joint pain).

3.5.2.1. Local Reactions

Local reactions reported in the e-diary are redness, swelling, and pain at the injection site.

Presence of Local Reactions (Proportion of Participants Reporting)

The participant will record the presence or absence of pain at the injection site in the e-diary as “Mild,” “Moderate,” “Severe,” or “None.” Redness and swelling will be measured and recorded in measuring device units (range: 1 to 21) and then categorized during analysis as mild, moderate, or severe based on the grading scale in Table 4. Measuring device units can be converted to centimeters according to the following scale: 1 measuring device unit = 0.5 cm. A participant with a severe (Grade 3 or above) local reaction will be prompted to contact the investigator to perform an unscheduled visit and assess the reaction.

Only an investigator is able to classify a maternal participant’s local reaction as Grade 4, after clinical evaluation of the maternal participant or documentation from another medically qualified source (eg, emergency room or hospital record) or, in the case of pain at the injection site only, contact with the participant. If a maternal participant experiences a Grade 4 local reaction, the investigator must immediately notify the sponsor. Grade 4 reactions will be collected on the unscheduled reactogenicity page and as an AE on the CRF. The AE event will be graded using the AE intensity grading scale as indicated in the table “Assessment of Intensity” in Section 10.3.3 of the protocol.

The presence or absence of each local reaction on a given day is defined as follows:

- = “Missing,” if the value is missing on a given day;
- = “Yes,” if the participant reports the reaction as “Yes” for redness or swelling (with a diameter of 2.5 cm or more) **or** “Mild,” “Moderate,” “Severe,” or “Grade 4” for pain at the injection site on a given day;
- = “No,” if the participant reports the reaction as “No” for redness or swelling **or** “None” for pain at the injection site on a given day.

For each local reaction, the derivation of whether or not the specific reaction occurred on “any day (Day 1-7)” will be made. The derivation of this variable is given in Table 2 below.

Table 2. Derived Variables for Each Local Reaction

Variable ^a	Yes (1)	No (0)	Missing (.)
Any day (Day 1-7)	Participant reports the reaction as “Yes” on any day from Day 1 through Day 7.	Participant reports the reaction as “No” on all 7 days or as a combination of “No” and missing on all 7 days.	Participant reports the reaction as missing on all 7 days.

a. The variable will be defined for each of the 3 local reactions.

For “any local reaction” on any day, a similar definition can be applied as given in Table 3 below.

Table 3. Derived Variables for Any Local Reaction

Variable	Yes (1)	No (0)	Missing (.)
Any day (Day 1-7)	Participant reports any redness or swelling >2.0 cm or “Yes” for pain at injection site on any day during Days 1 through 7.	Participant reports redness or swelling ≤2.0 cm or pain at injection site as “No” on all 7 days or as a combination of above and missing on all 7 days for all 3 local reactions.	Participant reports all of the local reactions as missing on all 7 days.

Grading Scale for Local Reactions

The grading of local reactions is listed below in Table 4.

Table 4. Grading Scale for Local Reactions

	Mild Grade 1	Moderate Grade 2	Severe Grade 3	Grade 4 ^a
Redness	>2.0 cm to 5.0 cm (5 to 10 measuring device units)	>5.0 cm to 10.0 cm (11 to 20 measuring device units)	>10 cm (>20 measuring device units)	Necrosis or exfoliative dermatitis
Swelling	>2.0 cm to 5.0 cm (5 to 10 measuring device units)	>5.0 cm to 10.0 cm (11 to 20 measuring device units)	>10 cm (>20 measuring device units)	Necrosis
Pain (at the injection site)	Does not interfere with activity	Interferes with activity	Prevents daily activity	Emergency room visit or hospitalization for severe pain at the injection site

- a. Only an investigator is able to classify a maternal participant’s local reaction as Grade 4, after clinical evaluation of the maternal participant or documentation from another medically qualified source (eg, emergency room or hospital record) or, in the case of pain at the injection site only, contact with the maternal participant. Grade 4 assessment should be made by the investigator using the AE severity grading scale. The assessment will be collected on the AE case report form.

Maximum Severity for Local Reactions

The maximum severity (highest grading) of each local reaction within 7 days after vaccination will be derived. The maximum severity will be derived as follows:

- = “Missing,” if values are missing for all days from Day 1 through Day 7;
- = 0, if the participant reports all reactions as “No” or a combination of missing and “No” for all days from Day 1 through Day 7;
- = *highest grade* (maximum severity) within 7 days after vaccination, if the answer is not “No” for at least 1 day.

Duration of Each Local Reaction

The duration of each local reaction will be calculated in days as (resolution date of reaction - start date of reaction + 1). Resolution of the reaction is the last day on which the reaction is recorded in the e-diary or the date the reaction ends if it is unresolved during the participant diary-recording period (end date collected on the CRF), unless chronicity is established. If there is no known end date, the duration will be considered unknown and set to missing.

Onset of Local Reaction

The onset day of each local reaction and any local reaction will be derived.

For the onset day of each local reaction, if participants report severity change of the local reaction, the first day of initial reporting of that specific local reaction will be counted.

For the onset day of any local reaction, the first day of reporting any severity of any local reaction will be counted.

In summary, the following variables will be derived for local reaction:

1. Presence or absence of each local reaction on each day (Days 1-7) after vaccination.
2. Presence or absence of each local reaction on “any day (Day 1-7)” after vaccination.
3. Presence or absence of any local reaction on “any day (Day 1-7)” after vaccination.
4. Maximum severity of each local reaction on “any day (Day 1-7)” after vaccination.
5. Duration of each local reaction after vaccination.
6. Onset day of each local reaction after vaccination.
7. Onset day of any local reaction after vaccination.

